4.1.3 Safety Population

The Safety population will be defined as all randomized participants who received at least one dose of study drug and will be based on actual treatment received. Screen failures and randomized subjects who did not receive any medication will be excluded from the safety analysis set.

All safety analyses will be based on the Safety population.

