16. STATISTICS

All data will be handled and processed according to the Sponsor's representative standard operating procedure (SOPs), which are written based on the principles of GCP.

A SAP, containing the detailed planned statistical methods, will be finalized prior to locking of the study database for the final analysis and will form the basis for the programming of the displays and analyses of the final study data. All statistical calculations will be performed using SAS® (SAS Institute Inc., Cary, NC, USA) or similar software. No formal hypothesis testing will be performed, and all analyses will be descriptive in nature.

Statistical methods will be further outlined in the SAP and approved by the Sponsor prior to any analysis. Procedures outlined in the SAP will supersede protocol specified statistical methods in the event of divergence.

Results will be analyzed and presented by stage of the study and dose group.

Descriptive statistics will be used to summarize the safety and efficacy data. No formal hypothesis testing is planned, and dose comparisons will be exploratory in nature. No adjustments will be made for missing or incomplete data, except for missing efficacy data, which may be imputed using multiple imputation.

The Baseline value is defined as the last available result collected/derived prior to the first treatment administration.

The change from Baseline value is defined as the difference between the result at the post-Baseline time point and the Baseline value.

Descriptive statistics will consist of the number of observations (n), mean, SD, minimum, median, and maximum for continuous data. Where applicable, 95% CIs for the mean may be presented.

Categorical data will be summarized using counts and percentages. Unless specifically stated otherwise, the denominator for all percentage calculations will be the number of subjects in the treatment group for the specific analysis set. Where applicable, 95% CIs (Clopper-Pearson) may be presented.

All collected and derived data will be listed.

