16.1.2. Safety Population

All subjects who receive at least one confirmed dose of IP will be included in the Safety population. Subjects will be analyzed according to the treatment they actually receive. The safety population will be used for summaries and listings of safety, tolerability, and drug exposure data.

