Subjects will be screened for inclusion and exclusion criteria during a 28-day screening period (Day -28 to Day -1). At the Treatment visit (Day 1), eligible subjects will be sequentially assigned to receive 1 course of allocated CBL-514 dose.

Subjects will visit the site on each of the study visits. Subjects will remain onsite for observation for at least 1 hour after the administration of CBL-514, or longer at the discretion of the Investigator and until all planned assessments for the visit are completed.

Subjects who are withdrawn from the study earlier than planned should attend an ET visit as soon as possible after early withdrawal, no later than 6 weeks from the last dose received.

A subject diary will be provided to each subject, to record if there are any changes to the injection site/s or any discomforts from Day 1 until last clinic visit or when all ISRs have resolved or stabilized. Subjects will be instructed to bring the subject diary with them for all visits to the clinic.

During Stage 1 of the study, the SRC will meet after all subjects in a dose group have completed the Week 1 visit. The SRC will review all reported AEs, AESIs, laboratory trends, and vital signs of all subjects from each dose group. Based upon review of available safety and tolerability data from each preceding dose group, the SRC will make a decision on progressing to the next dose group.

The safety and tolerability data of CBL-514 from Stage 1 will be reviewed by the SRC before commencement of Stage 2. A top-level summary of safety data will be submitted to the relevant IRB/IEC for review before proceeding to Stage 2 of the study.

Study visits and assessments for Stage 1 of the study will occur as delineated in the Schedule of Assessments.

Stage 2 (multiple-dose, randomized, single-blind, parallel, placebo-controlled study)

Stage 2 will be conducted as a single-blind study, with 1 CBL-514 group and 1 placebo group. Each subject will receive up to 4 treatments of allocated CBL-514 (2 mg/cm²) or placebo administered on abdomen, once every 4 weeks. The minimum dose is 300 mg per treatment and the maximum dose is 600 mg per treatment. The dose adjustment will depend on the level of fat accumulation on subject's abdomen at the discretion of the Investigator.

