2.3 Endpoints

2.3.1 Primary endpoints

Stage 1:

- Safety and tolerability following single dose of CBL-514 as assessed by recording of TEAEs, laboratory assessments, vital signs, ECGs, physical examinations, and injection site assessment.

Stage 2:

- The proportion of subjects who lose at least 150 mL of subcutaneous fat as measured by ultrasound from Baseline to follow-up visits compared with placebo. [Time frame: Visit 2 (Baseline), Visit 6, and Visit 7]

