2.5 Randomization

Stage 1 of the study will be open label with a total of 24 subjects sequentially enrolled in 4 dose groups (6 subjects in each group) to receive one course of allocated CBL-514 dose as presented in Table 1. Once deemed eligible for enrolment in the study, each subject will be assigned a sequential subject number prior to first dosing.

Stage 2 of the study will be a randomized, single-blind, parallel-group. Considering drop-out rates (16% CBL-514 group vs 44% placebo group), approximately 75 subjects are planned to be enrolled and randomized 2:1 (50 subjects in the CBL-514 group and 25 subjects in the placebo group) in order to have a total of at least 56 evaluable subjects in Stage 2 of the study. The dose of CBL-514 used in Stage 2 will be set no higher than the highest safe dose from Stage 1. Once deemed eligible for enrolment in the study, each subject will be assigned a sequential randomization number prior to first dosing.

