4.1.2 Full Analysis Set Population (FAS Population)

The full analysis set (FAS) population will be defined as all randomized subjects who receive at least one course of IP and contribute qualified baseline and at least one post-dose efficacy assessment measured by ultrasound.

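### SAP 4.1.3 admits only randomized participants to the Safety population, so read literally it leaves out all 24 non-randomized Stage 1 subjects; the wording needs correcting

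*SAP*

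**What the plan says.** SAP 4.1.3 sets the rule: "The Safety population will be defined as all randomized participants who received at least one dose of study drug". Its next sentence excludes screen failures and randomized subjects who were never dosed, and the section ends: "All safety analyses will be based on the Safety population".

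SAP 4.1.2 uses the same condition for the full analysis set: "The full analysis set (FAS) population will be defined as all randomized subjects who receive at least one course of IP", with qualifying ultrasound data in addition. SAP 4.1.4 then makes the Stage 1 Per Protocol set a subset of the FAS.

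On allocation, SAP 2.5 says: "Stage 1 of the study will be open label with a total of 24 subjects sequentially enrolled in 4 dose groups". SAP 2.1 says of Day 1 that "eligible subjects will be sequentially assigned to receive 1 course of allocated CBL-514 dose". SAP 2.5 gives Stage 1 subjects a sequential subject number; only Stage 2 subjects receive a randomization number.

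The protocol's definition is wider (16.1.2): "All subjects who receive at least one confirmed dose of IP will be included in the Safety population". Protocol 16 settles conflicts in the SAP's favour: "Procedures outlined in the SAP will supersede protocol specified statistical methods in the event of divergence".

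The Stage 1 primary endpoint (SAP 2.3.1) begins: "Safety and tolerability following single dose of CBL-514 as assessed by recording of TEAEs".

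**The concern.** The condition for entering the Safety population is one that no Stage 1 subject can meet, and safety is what Stage 1 was set up to measure. The protocol's definition works for both stages, but by the protocol's own precedence rule the narrower SAP text governs. SAP 13 declares no change to the planned analysis, and the change history for Addendum 1.0 covers only the removal of imputation, so the difference is not acknowledged anywhere.

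Someone has to apply the rule. SAP 5.1.2 calls for a count of each population and a listing of every participant's membership. For each Stage 1 subject the Safety flag must either follow the definition, which empties the tables for the stage's primary endpoint, or depart from it. Membership of the set behind a primary endpoint should come from the text and not from a programmer's inference.

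**Working it through.** No power, alpha or effect size enters. The check applies each definition, word for word, to the planned subjects.

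**Inputs**
- Stage 1: 4 groups of 6, open label, assigned in sequence (SAP 2.1, 2.5). 4 × 6 = 24, the plan's own figure.
- Stage 2: 75 randomized 2:1, 50 to CBL-514 and 25 to placebo (SAP 2.4, 2.5). 24 + 75 = 99, again the plan's figure.
- Assumption: every planned subject receives at least one dose.

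**Counts under each Safety or ITT rule**

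| Rule | Condition | Stage 1 | Stage 2 |
|---|---|---|---|
| Safety, SAP 4.1.3 as written | randomized and dosed | 0 of 24 | 75 of 75 |
| Safety, Protocol 16.1.2 | dosed | 24 | 75 |
| ITT, SAP 4.1.1 | assigned or randomized | 24 | 75 |
| Safety, SAP 4.1.3 corrected | (assigned or randomized) and dosed | 24 | 75 |

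The FAS rule in SAP 4.1.2 also starts from randomized subjects. The Stage 1 FAS is therefore 0 as written, and so is the Stage 1 PP set drawn from it.

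**Can randomized be read as enrolled?** Not comfortably. SAP 4.1.1 names assigned and randomized subjects as alternatives, and SAP 2.5 reserves randomization numbers for Stage 2.

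**What rests on the Safety population in Stage 1** (SAP 17, table list)
- Exposure: 14.1.3.1 (1 table)
- Prior and concomitant medications: 14.3.1.1 and 14.3.2.1 (2)
- Adverse events: 14.3.3.1.1 to 14.3.3.10.1 (10)
- Blood tests: 14.3.4.1.1 and 14.3.4.2.1 (2)
- Urinalysis, vital signs and ECG: 14.3.5.1.1, 14.3.5.2.1, 14.3.5.3.1.1 and 14.3.5.3.2.1 (4)

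Total: 1 + 2 + 10 + 2 + 4 = 19 tables, each labelled Stage 1 and Safety Population. The adverse event, drug administration and medication listings also use this set.

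**What rests on the FAS or PP set in Stage 1.** All four Stage 1 efficacy tables (14.2.1.1.i, 14.2.2.1.i, 14.2.3.1.i, 14.2.4.1.i) are on the ITT population, as SAP 10 specifies. No Stage 1 FAS or PP table is listed. Protocol 16.3.1 does allow a PP repeat where relevant, so the Stage 1 PP set would matter only if that repeat were run.

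**The case against.** The strongest reply is that the SAP, read as a whole, plainly means to include Stage 1. Nineteen tables could not be produced otherwise. SAP 3.6 lists the four Stage 1 dose groups and a Stage 1 overall column. SAP 4.1.4 writes PP criteria for Stage 1 as a subset of the FAS, which presupposes Stage 1 subjects in the FAS. The exclusion sentence in 4.1.3 does not name dosed Stage 1 subjects. All of this stands, and a programmer would very likely include the 24.

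A reader might infer that the Stage 1 primary safety analysis will be reported with no subjects, or that Stage 1 was left out on purpose because the ITT text shows the drafters knew the difference. The documents support neither. The table list points the other way. The ITT paragraph itself goes on to analyse everyone by randomly assigned treatment, which does not fit Stage 1 either and suggests loose, Stage 2-minded drafting.

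A reader might also infer that any departure would go unrecorded. Protocol 16.1 has membership determined before the final analysis; SAP 14.2 has the populations approved before it and deviations documented in the study report. An empty Stage 1 set would be noticed.

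Nor does Stage 1 safety oversight hang on this sentence. Dose escalation and the move to Stage 2 rest on Safety Review Committee review of all subjects in each dose group. Stage 1 laboratory, vital-sign, ECG and physical-examination listings use the ITT population.

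What remains is that clear intent makes the correction easy but does not make the governing sentence right.

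**Conclusion.** SAP 4.1.3 is wrong as written. Applied literally it admits 0 of 24 Stage 1 subjects to the population for that stage's primary endpoint, contradicting both Protocol 16.1.2 and the SAP's own table list. The zero does not depend on the dosing assumption or on the exact Stage 1 enrolment, since no Stage 1 subject is randomized; the 24 after correction assumes that all planned subjects are dosed.

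Its weight is that of a drafting error in a controlling definition, to be corrected before populations are approved. It is not a biased method or a likely loss of data. It changes no Stage 2 result, sample size or error rate.

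The matching condition in 4.1.2 is a consistency point. It empties the Stage 1 FAS and PP sets on paper but feeds no listed Stage 1 table. It would be tempting to limit the Stage 1 FAS to Groups 2–4 (3 × 6 = 18 subjects) because SAP 10 rules out efficacy assessment for Group 1. Neither SAP 4.1.2 nor the protocol's population definitions contain that limit, so it is not part of this correction.

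**What to change.** In SAP 4.1.3, define the Safety population as *all assigned (Stage 1) or randomized (Stage 2) participants who received at least one dose of study drug*, keeping analysis by actual treatment. Restoring the all-dosed wording of Protocol 16.1.2 would do equally well.

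In SAP 4.1.2, make the same change from randomized to *assigned or randomized* and leave the dosing and ultrasound conditions as they are. The Stage 1 PP set then follows without further editing. How Group 1 stands under the ultrasound condition is for the sponsor to settle separately.

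Issue both changes with the next SAP revision, before the populations are approved under SAP 14.2. The cost is one phrase in each of two sentences. No listed table or sample-size figure changes, and there is no analytic downside.

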4.1.4 Per Protocol (PP) population

Stage 1:

1. A subset of FAS population
2. Subjects without any efficacy related major protocol violations
3. Subjects who complete the proposed dosing schedule of study drug (i.e. did the participant complete the study= Yes) and complete all follow-up visits after treatment
4. Subjects whose body weight remain stable throughout the study, identified as having body weight change < 3% based on Day 1 body weight. When the body weight data is missing, the subject will be regarded as having a stable body weight.

However, a subject who was discontinued due to an AE, or died before the required exposure could be met, will still be included in this population.

Stage 2:

1. A subset of FAS population
2. Subjects without any efficacy related major protocol violations
3. Subjects who complete all proposed dosing schedules of study drug (i.e., did the participant complete the study= Yes) and complete 2 follow-up visits after treatment (including the subject who has dose adjustment judged by the Investigator)
4. Subjects have all visits of IP administration within 6 weeks

5. Subjects whose body weight remain stable throughout the study, identified as having body weight change < 2.5 kg compared to last visit and change of body weight < 3 kg compared to Day 1 body weight
6. Subjects whose Visit 6 is performed 3 to 5 weeks post final treatment
7. Subjects whose Visit 7 is performed 7 to 9 weeks post final treatment

However, a subject who was discontinued due to an AE, or died before the required exposure could be met, will still be included in this population. (Such subject should continue to satisfy the PP population criteria outlined in items 1, 2 and 5 above; Furthermore, if scheduled visits attended by the subject. That must adhere to the specified time frames outlined in items 4, 6 and 7 above.)

5. PARTICIPANT DISPOSITION AND ANALYSIS POPULATIONS

Participant disposition and analysis population analysis will be based on all subjects. Participant disposition and analysis populations will be summarized descriptively as described in section 3.1 (categorical descriptive analysis).

5.1.1 Participant Disposition

Participant disposition will include the number of subjects screened, enrolled, screen fails, participants who completed the study as planned and participants withdrawn from the study, as well as the primary reason for early termination. Participant disposition will be summarized descriptively.

5.1.2 Analysis Populations

The number of participants included in each study populations will be summarized descriptively.

In addition, the inclusion of each participant into/from each of the defined analysis populations will be presented in the by-participant data listings.

6. PROTOCOL DEVIATIONS

Protocol deviations will be presented for each participant in the by-participant data listings.

Prior to database lock, all protocol deviations will be reviewed by medical monitors and assigned a status of Important if qualifying as such. i.e., efficacy related major protocol violations.

Protocol deviations and important protocol deviations will be categorized as noted in the Protocol Deviation Management Plan version 2.0 dated 13May202.

7. DEMOGRAPHIC AND BASELINE INFORMATION

Demographic and baseline information will be summarized descriptively as described in section 3.1.

7.1 Demographics

Demographic variables will be summarized using descriptive statistics in accordance with section 3.1 based on the ITT population. The following demographic parameters will be analyzed:

Continuous descriptive analysis:

- Age (years)
- Height (cm)
- Weight (kg)
- BMI (kg/m²)

Categorical descriptive analysis:

- Sex
- Race
- Ethnicity

Demographics variables will also be listed by stage and treatment group (section 3.7) under ITT population sorted by subject ID.

7.2 Medical /Surgical history

Medical / Surgical history will be coded using the most current Medical Dictionary for Regulatory Activities (MedDRA®). Subjects with any past or ongoing medical history will be summarized by system organ classification (SOC) and preferred term (PT) using descriptive statistics in accordance with section 3.1 for the ITT population by treatment groups defined in section 3.7. Medical history will be ordered from the highest frequency in the overall column by SOC and PT.

Medical history listings will be provided by stage and treatment arm (grouping provided in section 3.7) sorted by subject ID for the ITT population, along with ongoing status of medical history and age/sex of the subject.

7.3 Viral Serology

Hepatitis B, Hepatitis C and Human Immunodeficiency Virus (HIV) results will be presented by stage and treatment arm sorted by subject ID for the ITT population.

7.4 Pregnancy

Listing for pregnancy results will be provided by stage sorted by subject ID for the ITT population.

7.5 Follicle Stimulating Hormone Testing

Women not of childbearing potential must be post-menopausal (defined as at least 50 years with cessation of regular menstrual periods for at least 12 months with follicle stimulating hormone > 40 IU/L). Post-menopausal status will be confirmed through testing of FSH levels at Screening. FSH results obtained will be presented in the by-participant data listings only.

7.6 Eligibility

Participant eligibility will be listed in a data listing.

8. TREATMENT EXPOSURE

Treatment exposure (total number of injections, total volume administrated, total Dose administrated) will be summarized using descriptive statistics in accordance with section 3.1 based on the Safety population. All study drug administration information (study drug administered (Yes/No), reason not administered, start and end date and time of administration, Lignocaine application, total volume administrated, total number of injections, study drug given per protocol (Yes; details of administration/No; Reason not given per protocol) will be presented in the by-participant data listings.

Total administrated dose can be calculated as below:

$$\text{Total Dose Administrated (mg)} = \text{Total Volume Administered (mL)} \times 5 \text{ mg/mL}$$

9. PRIOR AND CONCOMITANT MEDICATIONS

Prior and concomitant medications will be coded using the most current version of the World Health Organization Drug Dictionary (WHODD). Medications will be mapped to the Anatomical Therapeutic Chemical (ATC) Level 4 and preferred term (PT), as the primary interest for the analysis.

The prior and concomitant medications and therapies are defined as follows.

1. Prior Medications: Prior medications are defined as any medication where the use was stopped prior to the first administration of the study medication.
2. Concomitant Medications: Concomitant medications are defined as any medication (other than the study drug) that was used at least once after the first administration of the study drug. If the end time of the medications is unknown, medications that were stopped on the same date as the first study drug administration will be defined as concomitant medications. If a clear determination cannot be made (partial medication end dates) the medication will be classified as concomitant.

The prior and concomitant medications/therapies are exclusive with each other.

Prior and concomitant medications will be summarized by Anatomical Therapeutic Chemical (ATC) class Level 4 and PT as noted in section 3.1 (categorical descriptive analysis) for the Safety population. Participant who used the same medication on multiple occasions will only be counted once in the specific category (PT). PTs will be sorted alphabetically. In addition to the summaries by the coded terms, the number of participants who used at least one concomitant medication during the study will be presented.

Prior and concomitant medications will be presented in the by-participant data listings for the Safety Population. Listing will include concomitant medications/therapy classification, medication taken, start and end date/time, ongoing status, reason for administration, dose, unit, dose form, frequency, and route of administration.

10. EFFICACY

Efficacy will be analyzed in both Stage 1 and Stage 2 of the study. All ultrasound data collected at scheduled and unscheduled visits will be included in the listings, but only results collected as scheduled visits will be included in the summary tables.

Stage 1

Efficacy endpoints to be analyzed in Stage 1 are:

1. Reduction of subcutaneous abdominal fat thickness as measured by ultrasound compared with Baseline (Week 4 vs Baseline)
2. Reduction of subcutaneous abdominal fat volume over the treated area as measured by ultrasound compared with Baseline. (Week 4 vs Baseline)

*Note: no efficacy assessments will be done for Group 1 of Stage 1 study. All the information collected for thigh fat thickness will be presented in by-subject listing sorted by subject ID for the ITT population.

- The subcutaneous abdominal fat thickness and fat volume (as defined in section 3.2) at baseline, and Week 4, along with the change and percentage change of fat thickness and fat volume from baseline will be summarized using descriptive statistics in accordance with section 3.1.
- Within-treatment analysis will be performed by paired t-test for Week 4 vs baseline for reduction of subcutaneous fat thickness and fat volume. An estimate of the mean difference in subcutaneous fat thickness and fat volume between baseline and Week 4 along with its 95% CI and corresponding p-value will also be provided. No claim can be made on these p-values based on this efficacy analysis as it is exploratory in nature. These p-values should be used wisely.

The analysis set for the primary efficacy analysis is the ITT population

Stage 2

Primary efficacy endpoints to be analyzed in Stage 2 are:

1. The proportion of subjects who lose at least 150 mL of subcutaneous fat as measured by ultrasound compared with placebo.

Secondary efficacy endpoints to be analyzed in Stage 2 are:

2. Reduction of subcutaneous fat volume over the treated area as measured by ultrasound compared with Baseline
3. Reduction of subcutaneous fat volume over the treated area as measured by ultrasound compared with placebo
4. Number of treatments required to first occurrence of reducing at least 150 mL of subcutaneous fat volume over the treated area as measured by ultrasound in CBL-514 group.
5. The proportion of subjects who lose at least 200 mL of subcutaneous fat as measured by ultrasound compared with placebo

- A summary table presenting the number and proportion of subjects who lose at least 150mL and subjects who lose at least 200 mL of subcutaneous fat volume over the treated area together with two-sided Clopper-Pearson 95% confidence intervals for each treatment group defined in section 3.7 will be produced.
- For the subcutaneous fat volume as measured by ultrasound data, summary statistics (as described in section 3.1) will be presented for values and change from baseline value at each visit.
- If the assumptions met, the Mixed-Effect Model Repeated Measurement (MMRM) will be used to assess the change over time in the CBL-514 and placebo treatment arms for the abdominal subcutaneous fat volume. The assumptions for MMRM can be checked as described in section 16.3. There will not be any alternative method used if assumptions of model-based analysis are not satisfied.

The model will include the following fixed factors/covariates:

- o Baseline subcutaneous fat volume,
- o Treatment Group,
- o Study Visit,
- o Treatment Group and Study Visit interaction term;

Subject as random effect and repeated visits will be also included in the model.

Unstructured within-subject covariance structure (TYPE=UN) will be selected for the model initially which makes no assumption about the relationship in the correlation among visits. If it leads to non-convergence, the following covariance structures will be explored: first order autoregressive (AR (1)), Heterogenous Toeplitz, Toeplitz, and compound symmetry, if appropriate. If the model does not converge, alternative covariance structures will be investigated. The Akaike Information Criteria (AIC) will be used to select the best model (smaller is better).

If model does not converge after the above, a standard regression model will be fitted at each time point using the same covariates as described above.

The Kenward-Roger (Kenward and Roger 1997) approximation will be used to estimate denominator degrees of freedom for tests of fixed effects.

Also, if the model is complex, simpler model will be explored.

The LS mean change from baseline, along with corresponding 95% CI and p-values for each treatment arm for Visit 3, Visit 4, Visit 5, Visit 6, and Visit 7 will be presented. In addition, the difference in change from baseline at Visit 6 and Visit 7 for CBL-514 600 mg versus placebo will be provided for the ITT population and repeated for PP Population.

No claim can be made on these p-values based on this efficacy analysis as it is exploratory in nature. These p-values should be used wisely.

The SAS code sample that can be used to implement the above MMRM analysis is given below:

```
PROC MIXED DATA= input_data;
CLASS treat (ref= 'Placebo') visit (ref='Baseline') usubjid;
MODEL chg= base treat visit treat*visit /ddfm=kr Solution CL;
REPEATED visit/subject=usubjid type=UN;
LSMEANS treat*visit/pdiff CL alpha=0.05;
LSMENAS visit/cl;
ods output lsmeans=lsmeans diffs=diffs;
run;
```

- The initial visits during which a subject experience a subcutaneous fat volume loss of 150 mL or more will be marked as flagged. For each subject, the number of treatments administered until the first flagged visit will be recorded and summarized descriptively along with the number of injections, volume and dose administered in accordance with Section 3.1. In cases where the subject is scheduled to receive the study treatment on the same date as the first flagged visit, that treatment will not be included in the count.

All the summary and analysis tables will be done for ITT and PP population for treatment groups defined in section 3.7.

All analyses will be performed without adjustment for multiple endpoints.

